We will use Brainsight™ neuronavigation to deliver stimuli on a grid in 1-cm steps in the coronal and sagittal planes, over the region of the primary motor cortex in the affected hemisphere. TMS will be delivered using a MagPro X100 stimulator with a 5 cm diameter figure-of-eight coil, held tangential to the skull and aligned in the para-sagittal plane with the handle rotated 45° lateral. Surface electromyographic (sEMG) recordings will be made from electrodes positioned over the muscle belly of the right flexor carpi radialis (FCR) muscle. EMG signals will be amplified (x1000) and band-pass filtered between 20 and 1000 Hz, before being digitized at 2000 Hz for 100 ms following each stimulation, using a Cambridge Electronic Design (CED) acquisition system. The optimal site of stimulation for FCR will be determined from initial exploration, and used throughout the experiment.

Resting Motor Threshold (RMT): Motor evoked potentials (MEP) recorded via surface EMG during the torque recordings, will be analyzed for peak-to-peak amplitude. The lowest stimulus intensity evoking a MEP of 50 μ V in at least five of ten trials in the relaxed muscle will be used. We will use 2% increments in stimulator output starting just below the intensity determined from initial exploration. Motor threshold is considered to reflect membrane-related intrinsic neuronal excitability. Ten MEP responses with single stimuli delivered at 120% RMT intensity will be recorded, to determine if a change in amplitude is observed at each time point.

Intracortical Inhibition: A single pulse TMS stimulus can be inhibited or facilitated if preceded by a subthreshold conditioning stimulus (Short Interval Cortical Inhibition SICI, 3msec inter-stimulus interval) is an accepted measure to determine if changes in corticospinal output are related to altered intracortical excitability. We will record 10 test MEPs, and 10 conditioned MEPs (80%RMT conditioning TMS intensity, test intensity adjusted to give 1mV amplitude MEPs) for SICI. Conditioned and unconditioned pulses will be randomly presented.

The frequency of TMS stimulation will not exceed 0.2 Hz, as this will avoid cumulative effects of the stimulation during assessment.

Transcranial Direct Current Stimulation (tDCS) Application

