Methods to address specific aim 1: We will compare demographic, clinical, kinematic, and tDCS variables between intervention groups using t-tests to compare means and chi-squared tests to compare proportions; where continuous data is non-parametric as defined by Shapiro-Wilk or Q-Q plots, we will use Kruskal Wallis tests. To assess the univariate relationship between treatment group and upper limb Fugl-Meyer score, repeated measures ANOVA will be used in order to account for longitudinal evaluations. Multivariate methods will include linear mixed models and ANCOVA to adjust for interactions or other covariates potentially contributing to the association between treatment and outcome. Further, Pearson correlation coefficients will be assessed to identify any linear association between kinematic, clinical and tDCS data points. The Spearman Rank correlation coefficient will be used for non-normally distributed variables. Like the Fugl-Meyer, secondary outcome measures, Wolf Motor Function, Barthel Index and Stroke Impact Scale are scored on a continuous scale and thus, will be analyzed as above. The MRC is scored on a scale from 0-5; Fisher analyses will be used to look for differences in strength between groups.

Specific Aim 2 (Kinematic): Determine if there is a statistically significant difference in a) mean speed, b) peak speed, c) smoothness, d) aim, and e) deviation from the straight line between subjects trained with and without tDCS prior to robotic training. This will be determined for both the trained tasks, as well as for the untrained, circle-drawing task. We will also include a static and dynamic quantitative measure of strength using the robotic device.

Methods to address specific aim 2: To assess the univariate relationship between treatment group and outcome, repeated measures ANOVA will be used in order to account for longitudinal evaluations. Multivariate methods will include linear mixed models and ANCOVA to adjust for interactions or other covariates potentially contributing to the association between treatment and outcome.

Specific Aim 3 (Neurophysiology): Determine if there is a statistically significant difference in: a) RMT, (b) MEP amplitude at 120% RMT, and c) SICI between subjects trained with and without tDCS prior to robotic training, both immediately following the training regimen, and 6 months later.

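### The EMG record specified for TMS begins at the pulse, so it holds no pre-stimulus baseline with which to verify the relaxed-muscle condition for RMT or to clean trials afterwards

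*Combined protocol and SAP*

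**What the plan says.** All recording details are in the TMS Evaluation section of the combined protocol and SAP.

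- **Acquisition** (Motor cortex stimulation and electromyography): after amplification and filtering, the signal is "digitized at 2000 Hz for 100 ms following each stimulation". This is the only EMG window the plan gives.
- **RMT** (Resting Motor Threshold): the lowest intensity that evokes a 50 µV MEP "in at least five of ten trials in the relaxed muscle will be used". The search moves in 2% steps of stimulator output.
- **Recording condition** (same paragraph): MEPs "recorded via surface EMG during the torque recordings, will be analyzed for peak-to-peak amplitude". The torque recordings are not explained.
- **MEP amplitude** (same paragraph): "Ten MEP responses with single stimuli delivered at 120% RMT intensity will be recorded".
- **SICI** (Intracortical Inhibition): "We will record 10 test MEPs, and 10 conditioned MEPs", with "80%RMT conditioning TMS intensity, test intensity adjusted to give 1mV amplitude MEPs". Conditioned and unconditioned pulses come in random order.
- **Use** (Statistical Considerations and Data Analysis, Specific Aim 3): the groups are compared on "a) RMT, (b) MEP amplitude at 120% RMT, and c) SICI between subjects trained with and without tDCS", after training and again six months later. The Aim 3 methods contain no data-cleaning step.

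The documents describe no pre-stimulus window, continuous EMG record, limit on background activity, relaxation check or rule for rejecting trials. Subjects are to be monitored continually during stimulation, but that statement is under Protection Against Risk and concerns safety.

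**The concern.** RMT is meaningful as a resting threshold only if the muscle is at rest when the pulse arrives. The usual evidence is the EMG just before the pulse, and the specified window leaves that stretch out. The target muscle is in a hemiparetic limb, where involuntary activity is a reasonable worry. The RMT paragraph adds to the doubt by placing MEP recording within torque recordings without saying how that fits with a relaxed muscle.

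Aim 3 uses these measures to establish plasticity with training and to characterise responders, and the RMT paragraph reads threshold as an intrinsic property of neurons. Background muscle activity is a competing explanation for a change in threshold. With ten trials per condition, a few active trials matter. RMT also sets two other intensities, so an error in it carries forward. A baseline that was never stored cannot be recovered at analysis.

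**Working it through.** **1. What is stored per trial.** Sampling rate × window = 2000 Hz × 0.100 s = 200 samples after the pulse. Samples before the pulse: 0.

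**2. Whether the post-pulse trace can stand in for a baseline.** The stretch before the response runs from the end of the stimulus artefact to MEP onset. The documents give neither time. Assume onset at 14–22 ms and an artefact lasting 3–10 ms:

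- shortest: 14 − 10 = 4 ms, or 8 samples;
- longest: 22 − 3 = 19 ms, or 38 samples.

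This stretch is short and follows the pulse, and the plan gives no rule for using it. It is weak information, but not none.

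**3. Sensitivity of the five-of-ten rule (illustration).** Let p be the true probability of a 50 µV MEP at a given intensity, and c the share of trials with enough background activity to be scored as a response. Assume every such trial is scored that way, which is the worst case. Then p′ = p + (1 − p)c, and the intensity passes with probability P(X ≥ 5), where X ~ Binomial(10, p′). The documents give no value for c, so a range is shown.

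| c (assumed) | p = 0.20: p′ | passes | p = 0.30: p′ | passes |
|---|---|---|---|---|
| 0 | 0.200 | 3.3% | 0.300 | 15.0% |
| 5% | 0.240 | 6.7% | 0.335 | 21.7% |
| 10% | 0.280 | 11.8% | 0.370 | 29.4% |
| 20% | 0.360 | 27.1% | 0.440 | 47.0% |

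**4. What this does to RMT.** The table gives pass rates at one intensity, not the shift in an Aim 3 outcome. For the shift, assume an ascending search in steps of 2 points of stimulator output, a probit response curve centred at 50% output with a spread of 2–4 points, and a start two spreads below the centre. Under the same worst-case scoring, mean RMT falls by about:

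- 0.2–0.4 points at c = 5%;
- 0.4–0.9 points at c = 10%;
- 1.0–2.4 points at c = 20%.

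Up to 10% contamination, the shift is less than half of one search step. A difference between arms would be smaller than these figures unless the contamination were confined to one arm.

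**5. How an RMT error carries forward.** If RMT is 1 point too low, the MEP test pulse is 1.2 × 1 = 1.2 points too low and the SICI conditioning pulse is 0.8 × 1 = 0.8 points too low. For MEP size two effects oppose each other: background activity during the test trials would tend to enlarge the response, and the lower test intensity would tend to shrink it. The net direction cannot be determined from the documents. For SICI the test response is set to 1 mV, so a 50 µV background is 50/1000 = 5% of it, and random ordering spreads background over both pulse types. SICI is thus largely protected from background at that level, apart from the error in its conditioning intensity.

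**The case against.** The strongest reply is that silence is being read as absence. The acquisition sentence says what is digitised; it does not say that the operator ignores the live EMG or delivers pulses into an active muscle. The plan requires a relaxed muscle and seats the patient comfortably, and the torque signal might show overt contraction. This stands in part. A reader might infer that relaxation cannot be checked at all, and the documents do not support that: live viewing is not described, but it is not excluded. What remains is that the stored EMG, as specified, gives no pre-stimulus evidence and no basis for a rule applied at analysis.

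Second, a reader might infer that any 50 µV deflection counts as a response. The criterion is an evoked MEP, so an alert assessor could disregard activity that does not look evoked. The plan gives no latency rule either way. The table's scoring assumption is therefore an upper bound, and its figures are illustrations.

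Third, rest is written explicitly only for RMT. MEP amplitude and SICI are tied to it through their intensities; their own muscle state is not stated.

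Fourth, both arms are recorded the same way by assessors who are to be blind to assignment (Blinding section). This stands: no evidence in the documents suggests that resting activity differs by arm.

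**Conclusion.** The point holds in a limited form. The specified acquisition window contains no pre-stimulus EMG, no rule elsewhere makes up for it, and the RMT paragraph does not reconcile a relaxed muscle with recording during torque measurement. The consequence is confined to Aim 3, where the main expected effect is added noise in RMT and in the two intensities derived from it. Its size depends on a contamination rate the documents do not give: over an assumed 5–20%, the pass rate at a true 20% response rate rises from 3% to between 7% and 27%, under worst-case scoring.

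A reader might go further and infer that Aim 3 would credit real tDCS with a cortical effect that is really a failure to relax. The documents do not support that. Such bias needs resting activity to differ by arm or to change with treatment, and even then the direction for MEP size is indeterminate. The Fugl-Meyer primary outcome and the sample size do not depend on this. It is a worthwhile improvement rather than a flaw that threatens the trial.

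**What to change.** In the EMG paragraph of TMS Evaluation:

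- start the acquisition window before the pulse, for example about 100 ms before;
- set a fixed limit on pre-stimulus EMG, reject trials above it blind to arm, and repeat the rejected pulses so that each condition keeps its ten trials;
- report rejection rates by arm and visit with the Aim 3 results;
- state the required muscle state separately for RMT, MEP amplitude and SICI;
- explain the torque recordings and reconcile them with the relaxed-muscle requirement.

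The cost is one acquisition setting and a few repeated pulses; no new equipment is needed. Because a missing baseline cannot be recovered, the change helps only recordings made after it. If pre-stimulus EMG is already stored, one sentence saying so answers the acquisition point; the limit, the rejection rule and the torque wording would still need stating.

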Previous studies indicate that stroke patients may differentially respond to non-invasive motor cortex stimulation protocols according to whether the lesion includes cortex, or is confined to white matter (52). Accordingly, we will use blocked stratified randomization to ensure our two comparison groups are balanced with respect to this known prognostic factor (cortical versus subcortical classification). Classification of this grouping will be assessed using CT or MRI with 'subcortical' defined as a stroke without involvement of cortical motor areas, and 'cortical' as infarction of cortical primary or secondary sensorimotor areas in addition to subcortical infarction.

Randomization of patients is performed by a statistician and epidemiologist, [name]. She will communicate the status to [name]. The switch is covered so that the therapist and the PI will not know the group assignment.

Blinding

The study is double-blind. All investigators interacting with patients will be unaware which patients are receiving real or sham stimulation. This includes the principal investigator and research fellows conducting robotic, neurophysiology or clinical assessments. The tDCS device has a coding option to program sham or real stimulation. [name], a histopathologist in [name] lab who is not involved with the robot project and has agreed to perform this toggling task will set the tDCS device for any particular patient. She knows [name] and we will establish communication between [name] – who will determine the randomization and [name] so that [name] and the Research Associate to be named will not have the patient's code. It is important to note that once the machine to deliver the transcranial direct current stimulation is toggled no further manipulation of the device is needed. The tDCSM operates automatically to deliver current or not. We will receive the coding option from the collaborating institution, and will reveal this information after analysis, unless there is a need to inform the PI in case of an adverse event. Patients will be asked at visit 9 and visit 15 (mid-point and end of the intervention period), whether they think they received real or sham stimulation.

Statistical Considerations and Data Analysis

Specific Aim 1 (Clinical): Determine if there is a statistically significant difference in the change in upper limb Fugl-Meyer and Wolf Motor Function score between subjects trained with and without tDCS prior to robotic training.

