Methods to address specific aim 3: To assess the univariate relationship between treatment group and outcome, repeated measures ANOVA will be used in order to account for longitudinal evaluations. Multivariate methods will include linear mixed models and ANCOVA to adjust for interactions or other covariates potentially contributing to the association between treatment and outcome.

POWER: Based on the previous study by Lo et al., we can expect twelve weeks of upper limb robotic training to result in a 2.88 change in the FM score (5). We estimated that tDCS plus robotics would result in a FM change score of 4.33. Using a two-sided alpha and a standard deviation of approximately 1.5, enrolling 56 subjects (28 per group) would give us 90% power to detect a difference in Fugl-Myer score of 1.45 between the intervention groups. To account for potential subject attrition, we aim to increase our sample size by 15% thus resulting in an enrollment goal to 66 (33 subjects per group).

Specific Aim 4 (Clinical): Determine if there is a statistically significant difference in the change in verbal expression scores on the Apraxia Battery for Adults (ABA-2) and Philadelphia Naming Test Short Form (PNT short form) between subjects with aphasia trained with and without tDCS prior to robotic training.

Methods to address specific aim 4: We will compare demographic, clinical, and tDCS variables between intervention groups with aphasia using t-tests to compare means and chi-squared tests to compare proportions; where continuous data is non-parametric as defined by Shapiro-Wilk or Q-Q plots, we will use Kruskal Wallis tests. To assess the univariate relationship between treatment group and ABA-2 score, repeated measures ANOVA will be used in order to account for longitudinal evaluations. Multivariate methods will include linear mixed models and ANCOVA to adjust for interactions or other covariates potentially contributing to the association between treatment and outcome. Further, Pearson correlation coefficients will be assessed to identify any linear association between clinical and tDCS data points. The Spearman Rank correlation coefficient will be used for non-normally distributed variables. Fisher analyses will be used to look for differences in strength between groups.

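### Randomisation is stratified by lesion type because response to stimulation may differ by it, but the plan pre-specifies no analysis that uses lesion type

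*Combined protocol and SAP*

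**What the plan says.** The Randomization section gives one reason for stratifying: "stroke patients may differentially respond to non-invasive motor cortex stimulation protocols according to whether the lesion includes cortex, or is confined to white matter". It then sets up blocked randomisation stratified by lesion class, read from CT or MRI, so that the arms are "balanced with respect to this known prognostic factor". Balance is the only purpose stated.

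Under Statistical Considerations and Data Analysis, the Aim 1 methods read: "To assess the univariate relationship between treatment group and upper limb Fugl-Meyer score, repeated measures ANOVA will be used". Further modelling consists of "linear mixed models and ANCOVA to adjust for interactions or other covariates potentially contributing to the association between treatment and outcome". The same sentence recurs for Aims 2, 3 and 4. Aim 5 is mainly descriptive. Lesion class is not named as a covariate, subgroup or interaction term under any aim.

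The POWER paragraph concerns the difference between whole arms: "we can expect twelve weeks of upper limb robotic training to result in a 2.88 change in the FM score", and "We estimated that tDCS plus robotics would result in a FM change score of 4.33". The target is therefore 1.45 points, with SD about 1.5 and 28 per group, raised to 33 per group for attrition. The test is called two-sided, but no alpha level is given.

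**The concern.** A prognostic factor predicts outcome whatever the treatment. An effect modifier changes how much the treatment does. The reason given for stratifying is of the second kind, while the use made of the factor suits the first. Balance protects the average comparison from chance imbalance, and a main-effect adjustment removes outcome variation between classes. Neither shows whether real minus sham differs between cortical and subcortical patients.

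Two things follow. First, if the effect does differ, the planned comparison reports an average whose size depends on the lesion mix enrolled. A null result could then not be separated, under the plan, from a benefit in one class only, and a positive result would not show where the benefit lies. Second, because no interaction is named, a lesion-type finding presented after unblinding would carry no more weight than any other subgroup chosen afterwards, although the randomisation was built around that factor.

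**Working it through.** **Inputs.** From the POWER paragraph: control change 2.88, tDCS change 4.33, difference 4.33 − 2.88 = 1.45, SD 1.5, 28 per arm, 15% attrition, 33 per arm enrolled. Assumed: alpha 0.05 two-sided (level not stated); share p of patients in the responsive class (lesion mix not given); the effect in the other class; equal SD and 1:1 allocation within classes.

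**The plan's own figure.** Standard error of the difference = 1.5 × √(2/28) = 0.401. Noncentrality = 1.45 / 0.401 = 3.62. Two-sample t-test power on 54 df is 94.4% at two-sided 0.05, against the stated 90%. The 90% is matched at two-sided 0.025 (90.2%) or with SD about 1.64 (90.1%). So 0.05 is an assumption here. Attrition agrees: 56 / 0.85 = 65.9, rounded up to 66.

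**Overall test if 1.45 points exists in one class and 0 in the other.** Average effect = 1.45 × p; noncentrality = average / (1.5 × √(2/n)); power from the noncentral t.

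| Share p | Average effect | Power, 28 per arm, 0.05 | Power, 33 per arm, 0.05 | Power, 28 per arm, 0.025 |
|---|---|---|---|---|
| 30% | 0.435 | 19% | 21% | 12% |
| 50% | 0.725 | 43% | 49% | 32% |
| 67% | 0.967 | 66% | 73% | 55% |
| 70% | 1.015 | 70% | 77% | 59% |
| 100% | 1.45 | 94% | 97% | 90% |

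At 0.05, power reaches 50% at p = 1.96 × 0.401 / 1.45 = 54% with 28 per arm, and at about 50% with 33 per arm. Mixing responders and non-responders also widens the tDCS arm's variance. At an even split this lowers the 28-per-arm figure slightly further, to about 40% (normal approximation).

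**Milder modification.** Even split, 1.45 in one class and 0.725 in the other: average (1.45 + 0.725)/2 = 1.0875, noncentrality 2.71, power 76% at 28 per arm.

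**Same average, unequal effects.** Even split, 2.9 and 0: average 1.45. The tDCS-arm variance is 1.5² + 1.45² = 4.35, so SE = √((4.35 + 2.25)/28) = 0.486. Power ≈ Φ(1.45/0.486 − 1.96) = 85%.

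**What an analysis by class would deliver** (even split, 14 per arm in each class).
- Within one class: 95% CI half-width = t(26 df) × 1.5 × √(2/14) = 2.056 × 0.567 = 1.17 points. Power for 1.45 is 69%.
- Interaction, 1.45 versus 0: SE = 1.5 × √(4/14) = 0.80; power ≈ Φ(1.45/0.80 − 1.96) = 44%.
- Interaction, 1.45 versus 0.725: power ≈ Φ(0.725/0.80 − 1.96) = 15%.
- Patients needed to test the 1.45-versus-0 interaction with 80% power: 16 × (1.5 × 2.80 / 1.45)² ≈ 135 evaluable, against 56 planned.

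**The case against.** The strongest reply has four parts.

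1. *The plan already allows for interactions.* The mixed-model and ANCOVA sentence covers them, and lesion class, as the only stratification factor, is an obvious candidate. A reader might infer from its absence that the trial will never estimate the effect by lesion type. The documents do not support that. They support only that no such analysis is pre-specified. The allowance does not close the gap, because it names no interaction, time point or quantity to report.

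2. *The dilution scenario is extreme.* The 1.45 points is the planned difference between whole arms, and giving one class nothing shrinks that average by construction. A reader might infer that an effect confined to one class would probably read as no effect. That needs the responsive class to be about half the sample or less, and the lesion mix is not given. At a two-thirds share power is 66%, at half-sized modification 76%, and with 2.9 and 0 about 85%. This stands: the figures are illustrations, not a forecast.

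3. *The analysis would not cure the dilution.* The overall test is unchanged, and interaction power of about 44% is no better than the overall 43% at an even split. This also stands. The gain is descriptive: two class-specific estimates with intervals, declared in advance.

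4. *Balance is a legitimate aim, and a factor can be both prognostic and a modifier.* Agreed. The existing label is incomplete but not shown to be wrong. The section says that patients may respond differently, so it would overread the text to say that the trial expects a difference.

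**Conclusion.** The point holds as a gap in pre-specification. The plan raises the possibility that response differs by lesion class, defines the classes and stratifies on them, but commits to no analysis that uses them. The overall comparison remains a valid test of the average effect.

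The possible size depends on quantities that the documents do not give. With alpha 0.05, SD 1.5, 28 per arm and an all-or-nothing effect of 1.45 points, overall power runs from about 19% to 70% as the responsive class goes from 30% to 70% of patients, against 94% if everyone benefits. Partial modification costs less. These figures show why the average alone could mislead. They do not measure what is lost by omitting the class analysis, which would leave overall power where it is. What is lost is an interpretable, pre-declared description of the effect in each class. The change is worth making because the strata already exist and the cost is small.

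**What to change.** In the Aim 1 methods:

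- Include lesion class, as the stratification factor, in the Fugl-Meyer model.
- Add one pre-specified arm-by-lesion-class term at the end of training, and name it as the only planned effect-modification analysis for this outcome.
- Report the real-minus-sham difference with its 95% CI in each class, labelled supportive, and keep the overall comparison as the primary test.

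In the Randomization section, describe lesion class as a possible effect modifier as well as a prognostic factor. Calling it an expected effect modifier would go beyond the section's own wording.

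The cost is a few sentences and one model, with no new data or patients. The downside is imprecision: intervals of about ±1.2 points per class at 14 per arm, and interaction power of about 44% even if the effect is wholly confined to one class. The text should say that a non-significant interaction is not evidence that the two classes respond alike.
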